The trial's primary outcome is medication adherence assessed at 12 months after randomization. For this outcome, medication adherence will be assessed using prescription claims data and measured as the mean PDC over the 12 months after randomization using the "average of averages" approach used for study eligibility. Adherence will be measured only for medications that qualified a patient for inclusion in the study and follow-up will begin at the point of randomization. Medications that were filled before randomization but had a supply that extended into the follow-up period will have their carry-over supply included in the adherence calculation.

In sensitivity analyses, we will measure medication adherence by calculating PDC beginning from the first fill of a medication after randomization until the end of the 12-month follow-up period. We will also repeat our analyses censoring patients with diabetes when they initiate insulin.

The secondary outcomes for the study include disease control and rates of healthcare utilization. Disease control will be measured as the following two different outcomes: (1) the proportion of patients achieving good disease control for all of their eligible conditions and (2) the proportion of patients achieving good disease control for at least one of their eligible conditions. Because disease control will be evaluated using biometrics that are collected during routine care rather than at study-prescribed intervals, we will use those values that are closest to each patient's 12-month end of follow-up period. If more than 10% of subjects have missing data we will repeat our analyses using multiple imputation

Rates of healthcare utilization will also be measured using administrative claims data and will include all-cause emergency room visits, physician office visits, and all-cause hospitalizations during the 12-month follow-up period.

Analytic plan

We will report the means and frequencies of pre-randomization variables separately for intervention and control subjects. Comparisons of these values will be performed using t-tests and chi square tests and their non-parametric analogs, as appropriate. The outcomes will be evaluated using intention-to-treat principles among all randomized patients.

In the primary analysis, the outcomes will be compared using generalized estimating equations with an identity link function and normally distributed errors to account for the clustering of subjects within practice sites. Our primary models will also adjust for the block-randomized design. If there are differences in baseline characteristics between study groups that are believed to be confounders of the intervention–outcome association, we will repeat our analyses after adjusting for these covariates.

A similar approach will be taken for the analysis of the secondary outcomes, except using logit link functions with binary errors and log link functions with Poisson errors, as appropriate for disease control and rates of healthcare utilization, respectively.

Several additional analyses will also be conducted. First, we will assess the correlation between calculated adherence based on insurer claims, self-reported adherence, and pharmacy transaction records (for patients filling prescriptions at Harvard Vanguard pharmacies). Second, we will use Markov modeling to assess the long-term impact of the intervention on cost, quality-adjusted survival, and cost-effectiveness of the intervention.

Sample size considerations

Our study should be sufficiently powered to detect small, clinically meaningful changes in the primary outcome. We powered the study to detect a 2.5% mean change in adherence between the intervention and control groups, assuming a standard deviation of 0.25 (a conservative assumption), clustering at the practice level with a design effect of 1.10, and a 15% non-differential loss to follow-up

rate. We assumed that 95% of potentially eligible intervention patients would be approved for study inclusion by their PCPs and that 50% of these patients would agree to a pharmacist consultation. With these assumptions, we estimated that we would need a total sample size of 4000 eligible patients to provide more than 80% power to detect differences in our primary study outcome of medication adherence. In other words, if those patients receiving the intervention demonstrate a 4.6% improvement in adherence, we will still have more than 80% power to detect an improvement of 2.5% in the overall sample. We also have substantial power to detect improvements in disease control, assuming a rate of controlled disease of 30% based on our pilot data.

Summary of changes to protocol

Date of submission	Description of modification	Rationale for modification	Approval date
11/20/2013	1- Adding new funding source: NIH - 1 R01 HL117918-01	Our NIH application will be funded	12/31/2013
07/01/2014	1- Adding that this will utilize HVMA sites, which is part of a larger organization (Atrius). 2- Including information clinical QI efforts have been removed and language simplified. 3- Discussing how roles will be determined from the pilot study 4- Updating the number of sites/ health centers 5- Discussing waiver of informed consent as well as stating that HVMA is relying on PHRC for IRB through an already existing umbrella IRB agreement between Partners and HVMA.	These changes have been updated as part of a continuing review as noted during the review process.	07/03/2014
03/13/2015	1- Updating definitions of "poor disease control" to reflect current practice guidelines. 2- Changing randomization process from the level of the physician to the level of the practice site. 3- Outlining the process by which physicians will approve patients for study participation in greater detail 4- Describing the actual tele-pharmacist intervention in more detail. 5- Increasing the number of patients included in the study has increased from 2000 to 3000, as this is roughly the number of eligible patients at our practice sites. 6- Uploading new documents including the letter notifying patients of the intervention, the research assistant telephone script, a list of FAQs that may be relevant when the research assistant (RA) calls a patient, a list of text messages that will be sent to patients, and the letter that will be sent to patients summarizing their new relevant clinical data.	Processes have been updated to reflect realistic work flows per the request of our partners at HVMA and the number of patients in the study based on eligible patients at the practice sites. We also included new documents that the research assistants will use to schedule patients for a telephone visit with their clinical pharmacist.	04/14/2015
05/19/2015	1- Slighting revising several documents including: the patient recruitment letter,	The first three documents propose minor updates,	06/22/2015

	research assistant FAQs, research assistant call script, and reminder call message to patients for their clinical pharmacist call.	such as "clinical pharmacist" as opposed to "pharmacist" and wording in an automatic reminder call that will be sent to patients prior to their appointments	
06/26/2015	1- Submitting revised text messages to be sent to patients who consent to receiving this service. 2- Including the text for a follow-up recruitment letter that will be sent to patients who could not be reached with the first recruitment letter mailing.	1- The new text messages better address specific barriers that may hinder optimal medication adherence. 2- The follow-up recruitment letter will allow us to re-contact patients who could not be reached with the first mailing.	07/02/2015
07/22/2015	1. Updating with Spanish-translated versions of the initial and follow-up patient recruitment letters 2. Updating the initial patient recruitment letter to include verbiage about the enclosed pillbox 3. Providing voicemail messages that RAs will leave to patients who could not be reached via phone 4. Adding additional questions to the RA FAQs 5. Revising the RA script	1. Spanish translations of the patient recruitment letters will allow us to appeal to patients whose primary language is Spanish. 2. We changed our workflow to mail a pillbox with the initial recruitment letter, so we want to reference this tool in the letter. 3. Voicemail messages will provide patients with the opportunity to return the RAs' calls. 4. Additional information in the RA FAQs will help RAs answer any questions about clinical pharmacist responsibilities. 5. Edits to the RA script reflect improved verbiage for recruitment.	08/04/2015
09/03/2015	1- Revising RA permissions to include access to contact patients via MyHealth, a secure, web-based program that allows patients to contact their physician's office about non-urgent medical matters. 2- Revising the re-contact letter that is already IRB approved to include reference	1- RA access to MyHealth would provide an alternative method to contact patients who could not be reached via [contact]

	to a small nominal collapsible drinking cup with pill container that will be included in the envelopes.	2- A small collapsible drinking cup with pill container could serve as a useful tool to increase adherence.	
01/12/2016	1- Updating the report card (progress report), which contains information on medication adherence and disease control according to each patient's claims data and most recent lab values.	The updated version of the report card reflects changes in both content and language. We included patients' most recently filled medications, last filled dates (according to claims data), and most recent lab values and incorporated more verbiage about medication adherence and next steps for better disease control.	01/25/2016
02/18/2016	1- Changing the enrollment number target from 3,000 to 4,080 patients to reflect findings from the first few months of enrollment.	After randomization, the referral rates by the PCPs were somewhat lower than originally estimated. Second, fewer patients randomized to the intervention were able to be reached by the RAs. We previously expected that 60% of patients would be reachable; that estimate is closer to 40%. Lastly, patients are censored when they lose insurance eligibility during follow-up, and more patients than originally estimated lose insurance. These affect the sample size estimates.	03/03/2016
06/29/2016	1- Adding the specific patient surveys and processes that will be conducted at the conclusion of the 12-month follow-up period for intervention patients who did not decline to speak to a clinical pharmacist. The surveys will be delivered via paper mailing with an online survey. Non-respondents will be mailed a second copy of the survey with an enclosed \$5 gift card as an incentive.	These surveys will be used to evaluate the effectiveness of the telepharmacist intervention on patient adherence and activation. The surveys will also be used to validate the adherence measures collected by retail pharmacy data and	07/22/2016

		pharmacy claims. We will compare adherence and assess the validity of these alternative measures.	
11/02/2016	1- Slightly modifying the protocol to clarify which data are being used by Partners investigators for the purposes of analysis. The present amendment includes this clarification in the protocol and in the related data forms, as applicable.	The study team will use HIPAA-limited PHI data from HVMA for the purpose of analyzing the study. The only PHI that will be shared with Partners investigators are dates (e.g., date of birth, admission/discharge dates, and dates of procedures).	12/16/2016
03/08/2017	1- Slightly modifying the protocol to clarify how the data are being used by Partners investigators for the purposes of analyses to inform the DUA between the BWH and HVMA.	Like other insurer administrative claims, these data may contain some diagnosis codes and procedures for potentially sensitive information (e.g., HIV diagnosis, reproductive history) as these are adjudicated claims from insurers. In this study, except for mental health conditions, we will not be specifically looking at these sensitive conditions as comorbidities, effect modifiers or outcomes. We are only planning to include these in aggregated counts of resource utilization.	04/27/2017

Original analysis plan

Outcome Measures

Adherence

Adherence will be assessed for each medication prescribed for diabetes, hypertension, and hyperlipidemia and compared between intervention and control patients. The main measure of patient adherence will be proportion of days covered (PDC) for the intervention and control groups, as assessed with HVMA pharmacy data. This will be computed using the date the prescription was filled, the 'days supplied' field in dispensed drug data, and the dates on which the prescription was refilled.

Clinical outcomes

Clinical outcomes of interest are the proportion of patients achieving the following clinical targets: HbA1c values for patients with diabetes, systolic and diastolic blood pressure for patients with hypertension, and LDL values for patients with hypercholesterolemia. All laboratory values are available within the EHR.

Statistical analyses

We hypothesize that the intervention will improve medication adherence and disease control.

All analyses will use intention-to-treat principles. Medication adherence based on the proportion of days covered will be compared using generalized estimating equations, with adjustment for the cluster and block randomized design. We will use an identity link function and normally distributed errors. The proportion of patients considered adherent by achieving clinical goals will be compared using a logit link function and binary distributed errors. We will censor patients if they die, lose insurance eligibility, or at the end of the study period. Analyses will be run unadjusted as well as after controlling for the potential confounders listed below.

Potential confounders

The independent variable of interest is exposure to the pharmacist intervention. We will measure several variables to assess the degree of balance between patients and physicians randomized to intervention versus control, to adjust for chance imbalances, and to assess whether the efficacy of the intervention is modified by particular patient characteristics. Patient demographic characteristics and major comorbid conditions, as identified based on EHR data, will be included as independent variables

HVMA currently has an existing clinical pharmacy program. These clinical pharmacists already work collaboratively with the primary care physicians in the clinics to provide patient education and advice around medication management. Primary care physicians can currently refer patients to the clinical pharmacist using an electronic referral in the electronic health record.

Final analysis plan

Sample size considerations

Our study should be sufficiently powered to detect small, clinically meaningful changes in the primary outcome. We powered the study to detect a 2.5% mean change in adherence between the intervention and control groups, assuming a standard deviation of 0.25 (a conservative assumption), clustering at the practice level with a design effect of 1.10, and a 15% non-differential loss to follow-up rate. We assumed that 95% of potentially eligible intervention patients would be approved for study inclusion by their PCPs and that 50% of these patients would agree to a pharmacist consultation. With these assumptions, we estimated that we would need a total sample size of 4000 eligible patients to provide more than 80% power to detect differences in our primary study outcome of medication adherence. In other words, if those patients receiving the intervention demonstrate a 4.6% improvement in adherence, we will still have more than 80% power to detect an improvement of 2.5% in the overall sample. We also have substantial power to detect improvements in disease control, assuming a rate of controlled disease of 30% based on our pilot data.

Outcome Measures

Primary outcome - Adherence

The trial's primary outcome is medication adherence assessed at 12 months after randomization. Medication adherence will be assessed using prescription claims data and measured as the mean PDC over the 12 months after randomization using the "average of averages" approach used for study eligibility. Adherence will be measured only for medications that qualified a patient for inclusion in the study and follow-up will begin at the point of randomization

Secondary outcomes

The secondary outcomes for the study include disease control and rates of healthcare utilization.

Disease control will be measured as the following two different outcomes: (1) the proportion of patients achieving good disease control for all of their eligible conditions and (2) the proportion of patients achieving good disease control for at least one of their eligible conditions. Because disease control will be evaluated using biometrics that are collected during routine care rather than at study-prescribed intervals, we will use those values that are closest to each patient's 12-month end of follow-up period up to a maximum of 15 months after randomization

Rates of healthcare utilization will also be measured using administrative claims data and will include all-cause emergency room visits, physician office visits, and hospitalizations during follow-up

Statistical analyses

We will report the means and frequencies of pre-randomization variables separately for intervention and control subjects. Comparisons of these values will be performed using t-tests and chi square tests and their non-parametric analogs, as appropriate. The outcomes will be evaluated using intention-to-treat principles among all randomized patients. In the primary analysis, the outcomes will be compared using generalized estimating equations with an identity link function and normally distributed errors to account

for the clustering of subjects within practice sites. Our primary models will also adjust for the block-randomized design. If there are differences in baseline characteristics between study groups that are believed to be confounders of the intervention–outcome association, we will repeat our analyses after adjusting for these covariates.

A similar approach will be taken for the analysis of the secondary outcomes, except using logit link functions with binary errors and log link functions with Poisson errors, as appropriate. If more than 10% of subjects have missing outcome data, we will repeat our analyses using the latest post-randomization lab values available and using multiple imputation.

Several additional analyses will also be conducted. First, we will assess the correlation between calculated adherence based on insurer claims, self-reported adherence, and pharmacy transaction records (for patients filling prescriptions at Harvard Vanguard pharmacies). Second, we will use Markov modeling to assess the long-term impact of the intervention on cost, quality-adjusted survival, and cost-effectiveness of the intervention

Potential confounders

We will measure several variables to assess the degree of balance between patients and physicians randomized to intervention versus control, to adjust for chance imbalances, and to assess whether the efficacy of the intervention is modified by particular patient characteristics such as baseline patient demographic characteristics, major comorbid conditions, medication use, and healthcare utilization as identified based on claims and EHR data.

Summary of changes to the analysis plan

Detailed sample size calculations are now provided which was not included in the original plan. The primary and secondary outcomes are now clarified along with the specific analytic strategy for these outcomes.

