We will enroll all primary care physicians and their eligible patients. Eligible patients include adults ≥ 18 years and < 85 years with a diagnosis of diabetes, hypertension, or hyperlipidemia; evidence of poor or worsening disease control (see Table 1); and evidence of medication non-adherence based on medication refill data. Disease control is evaluated using the most recent lab or blood pressure values in the electronic health record and is based on clinical guideline targets from the American Diabetes Association (ADA), the Eighth Joint National Committee (JNC 8) hypertension guidelines, and the American College of Cardiology/American Heart Association (ACC/AHA) cholesterol guidelines. Adherence is assessed using prescription claims data. HVMA prescription data are available with a one-month lag. For each medication used to treat any one of the targeted conditions, the proportion of days covered (PDC) is calculated as the number of days of medication that a patient filled between the first fill date and the randomization date divided by the number of days in that same period (up to a maximum of 365 days). We consider drugs that are chemically related and not intended for use in combination to be interchangeable (e.g., two different statins). We average the PDC for all medications used to treat a single condition (e.g., all oral hypoglycemics) and then calculate an overall average adherence for all of the conditions that a patient had at the time of their identification.

TABLE 1. Definitions of poor and worsening disease control

Condition	Age (years)	Poor control	Worsening control
Diabetes	...	Latest HbA1c > 8	Latest HbA1C $7.5 \leq \text{to} \leq 8$, and previous HbA1C 1% lower
Hypertension	≥ 60	Latest BP $> 150/90$	Latest BP $140/80 \leq \text{to} \leq 150/90$, and previous BP 20 mmHg lower
	< 60	Latest BP $> 140/90$	Latest BP $130/80 \leq \text{to} \leq 140/90$, and previous systolic or diastolic BP 20 mmHg lower
Hyperlipidemia	...	Diagnoses of ASCVD	...
	40-75	Type 1 or 2 diabetes and use of glucose lowering agent	...
	40-79	ASCVD risk $> 7.5\%$...
	...	LDL $> 190 \text{ mg/dl}$	Latest LDL $175 \leq \text{to} \leq 190$, and previous LDL 30 mg/dl lower

...= N/A; Abbreviations: HbA1c, glycosylated hemoglobin; BP, blood pressure; ASCVD, atherosclerotic

cardiovascular disease; LDL, low-density lipoprotein

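### The main disease-control models leave out baseline control, and no measured-value definition of good control covers every entry route

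*Combined protocol and SAP*

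**What the plan says.** **Outcome.** The Final analysis plan (Secondary outcomes) names two disease-control outcomes. The first is "the proportion of patients achieving good disease control for all of their eligible conditions"; the second asks for good control of at least one such condition. The Final protocol (Outcomes) says that "disease control will be evaluated using biometrics that are collected during routine care". Neither section attaches an HbA1c, blood pressure or LDL value to good control.

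**Entry.** Under Subjects, the Final protocol requires "evidence of poor or worsening disease control (see Table 1"). It adds: "Disease control is evaluated using the most recent lab or blood pressure values in the electronic health record", and this "is based on clinical guideline targets from the American Diabetes Association (ADA") and two other guideline bodies. The target values themselves are not given. Table 1 covers poor and worsening control only. Its hyperlipidemia rows for poor control are an ASCVD diagnosis; "Type 1 or 2 diabetes and use of glucose lowering agent" (ages 40 to 75); an ASCVD risk above 7.5% (ages 40 to 79); and LDL above 190 mg/dl.

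**Model.** The Final analysis plan (Statistical analyses) adjusts the primary models for the blocked design. Other covariates depend on a condition: "If there are differences in baseline characteristics between study groups that are believed to be confounders", the analyses are repeated with those covariates added. For disease control, "A similar approach will be taken for the analysis of the secondary outcomes", with a logit link. The Potential confounders section says that variables will be measured partly to adjust for chance imbalance. Its examples are demographics, comorbidity, medication use and utilization; baseline disease control is not among them.

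**Power.** Sample size considerations calls the power for disease control substantial, given a 30% control rate from the pilot. It states no difference to be detected.

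**The concern.** Where a patient starts on HbA1c, blood pressure or LDL probably says a good deal about whether that patient is in control 12 months later. A main model that omits this leaves predictable variation in the treatment comparison. With few randomized units, a chance difference in starting control between the arms is also plausible. The plan would then look at the imbalance, form a view on whether it confounds, and perhaps report a second result, with no rule for weighing the two.

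The outcome definition adds to this. If good control is not tied to measured values for each condition, the analyst must choose the classification, and the obvious sources for that choice classify the same patients differently. At stake are the precision and interpretability of both disease-control comparisons, not the adherence result.

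**Working it through.** **1. The plan's own figure.** Inputs from Sample size considerations: difference 0.025, SD 0.25, design effect 1.10, loss 15%, power 80%. Two-sided alpha 0.05 is assumed, since none is stated.
- Per arm: 2 × 0.25² × (1.960 + 0.842)² / 0.025² = 1570.
- With clustering: 1570 × 1.10 = 1727. With loss: 1727 / 0.85 = 2032. Total 4064, against 4000 stated (1.6% apart).
- Power at 4000 is 79.4%. The primary calculation reproduces within rounding and does not involve disease control.

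**2. The missing detectable difference.** The same design effect and loss are borrowed for disease control, which is an assumption.
- Effective patients per arm: 4000 × 0.85 / 1.10 / 2 = 1545.
- Solve Δ = 2.802 × √[(0.30 × 0.70 + p(1 − p)) / 1545] with p = 0.30 + Δ. At p = 0.347 the root is √(0.4366 / 1545) = 0.0168, so Δ = 0.047, or 4.7 points.
- Range: 4.2 points from a 20% base and 5.0 from 50%; 4.3 with no loss; about 5.5 if the design effect were 1.5 (4.71 × √(1.5 / 1.10); the 1.5 is purely illustrative).

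**3. Table 1 against the biometric statement.** Of the four hyperlipidemia rows for poor control, one contains an LDL value and three do not. That does not fit the statement in the same section that control is judged on laboratory or blood pressure values.

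**4. Possible readings of good control.**

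| Reading | Consequence |
|---|---|
| Neither poor nor worsening in Table 1 | An ASCVD-diagnosis entrant stays poor on lipids whatever the LDL. If eligible conditions are the qualifying ones, every patient is out of control on all of them at entry |
| Not poor in Table 1 | The ASCVD row is still blocked. A worsening entrant with, say, HbA1c 7.8 already counts as good for diabetes at entry |
| LDL not above 190 | Entrants by the three rows without LDL may already meet it at entry |
| Guideline targets | Named, but with no values and no link to the outcome; cannot be checked |

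**5. What the design balances.** Under Study design and randomization, 14 sites were randomized in four blocks, 14 / 4 = 3.5 sites per block on average. The blocks are formed by site size and by whether site pharmacists counsel patients directly. Neither factor is baseline control. That section gives differences between sites as its reason for blocking.

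**6. What is available.** Eligibility is assessed on the most recent values in the health record, so baseline HbA1c and blood pressure should largely be held. LDL may be absent for patients who entered by the three rows that do not need it.

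**The case against.** **The main model is already fixed.** It adjusts for block, and the covariate analysis only repeats it. A reader might infer that an observed imbalance picks the main result; the text does not support that. Nor does leaving out a prognostic covariate invalidate a randomized comparison. The list under Potential confounders is illustrative, so baseline control is not ruled out. All of this stands. What remains is that a probable strong predictor, largely in hand, is not planned into the main model, and its use depends on inspecting the arms.

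**Inverting Table 1 is nowhere stated.** The outcome text speaks of biometrics, and a diagnosis or drug-use row is not one. The Background describes patients who miss recommended clinical targets, which points to a target-based outcome. A reader might infer that ASCVD entrants are shut out of good lipid control; that follows only if Table 1 is inverted, and the documents do not say so. They do not settle on another reading either.

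**A careless covariate would not help.** Under the first reading in the table, control status at entry does not vary. Worsening versus poor does not separate the rows without LDL from the other poor rows, and a patient may be poor on one condition and worsening on another. A level in which no patient can have the outcome would cause quasi-separation in a logit model. These points are right and shape the fix.

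**Conclusion.** The concern holds for the two disease-control secondary outcomes. Always adjusting for baseline control is a better main analysis than an imbalance-triggered repeat and costs little. Table 1 and the biometric outcome need to be reconciled.

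The benefit of adjustment cannot be quantified from the documents. It rests on the judgement, which they do not test, that baseline control predicts 12-month control. A reader might go further and infer that many patients cannot change status, so that power falls well short. The documents give neither the shares by entry row nor a disease-control effect, and the 30% pilot rate may already include such patients, so no reduced power figure is justified. What can be said is that the claim of substantial power cannot be checked without a definition and a difference. The figure of about 4.7 points is a reference under the assumptions shown, not the plan's target.

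**What to change.** 1. **Adjustment.** In place of the imbalance-triggered rule, prespecify that the main models for both disease-control outcomes include one compact patient-level baseline term. An example is the number or share of the patient's eligible conditions out of control at baseline, on the measured-value definition used for the outcome. If that is constant at entry, use a baseline score of biometric distance from target. Keep all randomized patients, with imputation or a missing category where no baseline LDL exists. Hold the set to one or two terms because there are 14 clusters, and avoid any level in which the outcome is impossible. Report a standardized risk difference beside the odds ratio, because adjusted and unadjusted odds ratios are different quantities.
2. **Definition.** Before outcomes are compared by arm, the sponsor should reconcile Table 1 with the biometric outcome, so that a measured-value definition applies to each condition and every entry route. No threshold is proposed here.
3. **Power statement.** Give the detectable difference and its assumptions, or qualify the claim.

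The cost is SAP wording and a little programming on health-record values the trial already uses. The main drawback is that some baseline LDL values will be missing.
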